4.1.1.4 Secondary Definition of Progression-Free Survival

PFS will also be analyzed after censoring patients who either received subsequent therapy or had two or more missing tumor assessments prior to their disease progression or death. In this secondary definition, PFS will be measured as the time in months from randomization to the date of the first documented tumor progression or death due to any cause, provided death does not occur more than 10 weeks (2 or more assessment visits) after the last tumor assessment. Clinical deterioration will not be considered progression.

The following censoring rules will be applied for this definition of PFS:

- Subjects who receive subsequent anti-myeloma therapy prior to documented progression will be censored on the date of the last adequate tumor assessment prior to the initiation of the new therapy.
- Subjects who have an event (documented progression or death) > 10 weeks (2 assessment visits) after the last prior adequate tumor assessment will be censored at the last prior assessment.
- Subjects who neither receive subsequent therapy prior to progression nor have a progression event (including death) will be censored at their last adequate tumor assessment.
- In addition, subjects who do not have any post-baseline adequate tumor assessments and who do not die within 10 weeks of randomization will be censored on the date of randomization.

In all cases, if there are no adequate assessments for censoring then the patient is censored on the randomization date.

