5.1 Progression-Free Survival

The primary objective of the study is to compare the progression-free survival between the treatment arms in all randomized subjects. The number of events and power of this study were calculated assuming an exponential distribution for PFS in each arm.

The study will require at least 71 PFS events (progressions or deaths), for a two-sided experiment-wise $\alpha = 0.2$ log-rank test, to show a statistically significant difference in PFS between the treatment arms with 85% power when the true hazard ratio of the experimental arm to the control arm is 0.57. This is equivalent to demonstrating an improvement in median PFS from 4.0 months in the Pd arm⁹ to a median PFS of 6.8 months in the E-Pd arm.¹ A total of 105 subjects are to be randomized. Assuming approximately 10% of subjects may be lost to follow-up for the primary endpoint data, an additional 9 subjects would be randomized in the study. It is estimated that it would take approximately 9 months for full accrual of 114 subjects (assuming a fixed accrual rate of 13 subjects per month) and another 6 months to obtain the required number of events.

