7.4.6 Subsequent Anti-Myeloma Therapy

The number and percentage of subjects with any subsequent systemic anti-myeloma therapy, reason for first subsequent systemic anti-myeloma therapy regimen (Documented progression of disease, Clinical deterioration without documented progression, Maintenance therapy without disease progression or clinical deterioration, or Other) and all subsequent systemic anti-myeloma therapy agents given categorized using the BMS WHO drug dictionary will be presented by treatment group.

The number and percentage of subjects with any subsequent surgery, type of first subsequent surgery (Kyphoplasty, Orthopedic surgery, Debulking surgery or Other) will be presented by treatment group.

The number and percentage of subjects with any subsequent radiation therapy will be presented by treatment group.

A by-subject listing of all subsequent surgery, all subsequent radiation therapy, and all subsequent systemic anti-myeloma therapy will be provided.

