8.5 Day Conversion of Date Imputation

Conversion from days to months or years:

- 1 year = 365.25 days
- 1 month = 30.4375 days

Imputation for partial or missing progression dates:

- If only the day is missing, the 1st of the month will be used to replace the missing day.
- If the day and month are missing or a date is completely missing, the date of progression will be moved back to the last complete tumor assessment date.

In both the cases given above, the imputed date will still be considered an event.

Imputation for partial or missing death dates:

- If only the day is missing, the later of the last known alive date and the 1st of the month will be used to replace the missing day.
- If both the day and the month are missing, the later of the last known alive date and Jan 1st will be used to replace the missing information.

In both the cases given above, the imputed date will still be considered an event.

For partial dates of start of subsequent anti-myeloma therapy, the following conventions will be used:

- When the day is missing, the alternative therapy will be assumed to start on the first day of the given month if this day is later than the last dosing date. Otherwise the alternative therapy will be assumed to start on the day following the last dosing date.
- When the day and the month are missing, the alternative therapy will be assumed to start on the first day of the given year if this day is latter than the last dosing date. Otherwise the alternative therapy will be assumed to start on the day following the last dosing date.

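### In the secondary (sensitivity) PFS definition, a partial start date of subsequent therapy can be imputed before the progression that prompted it, so a known event is censored

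*SAP*

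**What the plan says.** SAP 8.5 gives the convention for partial start dates of subsequent anti-myeloma therapy. "When the day is missing, the alternative therapy will be assumed to start on the first day of the given month", on condition that this day is later than the last dosing date. If it is not, the start is set to the day after last dose. When both day and month are missing, the same logic applies with 1 January. Neither the progression date nor the reason for the switch enters the rule.

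The imputed date matters through SAP 4.1.1.4 (matching protocol 8.3.1.2): "Subjects who receive subsequent anti-myeloma therapy prior to documented progression will be censored on the date of the last adequate tumor assessment" before the new therapy. Under the primary definition in SAP 4.1.1.3, subsequent therapy does not censor.

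SAP 7.5.1 uses the secondary definition for sensitivity analyses, SAP 7.5.1.1 repeats the supportive models under it, and SAP 8.7 lists four top-line outputs based on it.

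The reason for the switch is already collected. SAP 7.4.6 summarises the "reason for first subsequent systemic anti-myeloma therapy regimen (Documented progression of disease" being the first category listed).

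**The concern.** A subject who changes therapy because of documented progression has, by definition, a start date after the progression date. The rule does not enforce that order. Its only lower limit is the day after last dose, which protects the order only if dosing ran to the day before progression or later. The subjects left exposed are mainly those who stopped treatment early and were followed for PFS, as protocol 3.6 and 5.4.1 require.

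For such a subject the secondary definition can read the switch as coming before progression, discard the progression, and censor at an earlier assessment. The ordering error runs one way: it can remove a progression but not create one. The censoring is informative, because the switch that triggers it followed a progression already on record. SAP 8.5 does impose a logical floor elsewhere: a partial death date is never placed before the last known alive date. Therapy start has no matching floor at progression.

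**Working it through.** **1. The plan's own figure.** SAP 5.1 plans 71 events for a "two-sided experiment-wise $\alpha = 0.2$ log-rank test" "with 85% power when the true hazard ratio of the experimental arm to the control arm is 0.57". Assuming 1:1 allocation (the ratio is not visible):

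- Schoenfeld: 4 × (1.2816 + 1.0364)² / (ln 0.57)² = 21.49 / 0.3160 = 68.0, so 69 events.
- Freedman: (1.2816 + 1.0364)² × (1.57 / 0.43)² = 71.6, so 72 events.
- Power with 71 events (Schoenfeld): 0.861.

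The figure reproduces. It belongs to the primary definition, where new therapy does not censor, so the imputation rule changes neither the 71 events nor the power.

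**2. The rule on single cases (day missing).**

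| Last dose | Progression | True start | Imputed start | Secondary PFS |
|---|---|---|---|---|
| 20 Feb | 20 Mar | 27 Mar | 1 Mar | event lost |
| 13 Mar | 20 Mar | 27 Mar | 14 Mar | event lost |
| 20 Mar | 20 Mar | 27 Mar | 21 Mar | event kept |
| 13 Mar | 20 Mar | 5 Apr | 1 Apr | event kept |

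**3. How often the order flips.** If last dose is two or more days before progression, the imputed start falls before progression exactly when the true start is in the same calendar month as progression and progression is not on the 1st. For a switch L days after progression, a month of m days has m − L − 1 such progression dates (none if this is negative). Taking progression as equally likely on each of the 1,461 days (48 months) of 2017–2020:

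- L = 7: (1461 − 48 × 8) / 1461 = 1077 / 1461 = 74%
- L = 14: (1461 − 48 × 15) / 1461 = 741 / 1461 = 51%
- L = 21: (1461 − 48 × 22) / 1461 = 405 / 1461 = 28%
- L = 28: (28 long months × 2 + 16 thirty-day months × 1) / 1461 = 72 / 1461 = 5%

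Coding the rule and running it over every day of those years gives the same shares for last dose 7, 14 or 28 days before progression. With last dose one day before, on, or after progression the share is 0%. With day and month both missing, the shares are 98%, 96%, 94% and 92%.

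**4. Events at risk.** The documents do not give the number of switchers, the rate of partial dates or the share stopping before progression. All three are assumptions here: 60 switchers, 10% or 30% with a missing day, half stopped before progression.

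- 10% partial: 60 × 0.10 × 0.5 = 3 exposed; 3 × 0.05 to 3 × 0.74 = 0.15 to 2.2 events lost.
- 30% partial: 60 × 0.30 × 0.5 = 9 exposed; 9 × 0.05 to 9 × 0.74 = 0.45 to 6.7 events lost.

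**5. With a floor at progression.** Rerunning the rule with the imputed start not allowed before the progression date gives 0% misordered in the scenarios rerun (switches 7 and 28 days after progression, at every last-dose timing). A floor at the day after progression is stricter by one day and gives the same result.

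**The case against.** The case against giving this weight is strong on reach.

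- **Role.** The affected analysis is labelled a sensitivity analysis and the supportive p-values are descriptive. Duration of response follows the primary definition (SAP 4.1.5). This stands.
- **The last-dose floor often works.** It is tempting to argue from the schedule that the error is routine: the last dexamethasone dose of a cycle is on Day 22, and Day 1 of the next cycle is 7 days later. That needs progression to be known on Day 1 before dosing. M-protein and light-chain results come from a central laboratory (protocol 5.4, 5.9). SAP 7.2.2 treats continued therapy as a relevant deviation only after 10 weeks from documented progression, because progression needs confirmation. SAP 4.1.1.2 dates progression at the earliest component. All three push last dose to or past the progression date. This largely stands, and early stopping is the more typical route.
- **Short lags may be rare.** If sites wait about one 4-week visit for confirmation, the 5% figure is the relevant one. The confirmation interval is not visible, so this is possible but not settled.
- **Cases can be found.** The SAP 7.5.1.1 listing shows PFS under both definitions with the censoring reason, and SAP 7.4.6 lists subsequent therapy. A cross-check would find discordant subjects, but nothing marks a start date as imputed.
- **The remedy has a cost.** The present rule does not depend on outcome. A floor tied to the recorded reason lets an investigator's entry decide event or censoring in an open-label trial.

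None of this answers the core point: a stated rule can contradict the recorded reason for the switch and give the wrong event status.

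**Conclusion.** The defect is real, confined to the secondary PFS definition and its supportive analyses, and minor. It requires a partial start date, a last dose at least two days before progression, and a switch in the same calendar month (or year, if the month is also missing). The conditional shares in the working follow from the rule, given uniformly distributed progression dates. The event losses, about 0.2 to 2 at 10% partial dates and 0.5 to 7 at 30%, rest on assumed inputs and cover the day-missing case only.

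A reader might infer that the primary result loses events or power. The documents do not support that, because primary PFS ignores subsequent therapy. A reader might also infer a biased hazard ratio. Nothing in the documents shows that partial dates or early stopping differ between arms, so neither the size nor the direction of any bias in the treatment comparison can be stated.

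**What to change.** Add to SAP 8.5, for the secondary PFS definition only: when the known part of the start date allows a start after documented progression, and the recorded reason for the first subsequent regimen is documented progression, use the later of the current rule's date and the day after progression. Keep the current rule for all other reasons. In the by-subject PFS listing of SAP 7.5.1.1, flag subjects whose secondary-definition status depends on an imputed start date.

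The cost is one sentence and one listing flag, using a field already collected. The downside is that, for these partial-date subjects, event status relies on an investigator-recorded reason in an open-label trial. The flag keeps that reliance visible.

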8.6 AE, Laboratory Results and Concomitant Medication

Safety data will be handled according to the BMS safety data conventions (described in “Analysis of Safety Data - Reference to CT SOP 109”). This document includes descriptions on how to analyze AE data as well as how to handle partial dates, missing dates, and unknown end dates when analyzing safety data.

The following dictionaries will be used to code medical terms and to derive toxicity grades:

- Adverse events and other symptoms will be graded according to the NCI CTC Version 3.0 and categorized according to the latest version of MedDRA at the time of analysis.
- Laboratory results will be classified according to the CTC Version 3.0 grading system.

- All medications will be coded as per the latest version of the WHO Drug dictionary at the time of analysis.
- Tables and listings for laboratory results will be available in SI units and US units.

8.7 Topline Analyses

Outputs covering the following topics will be included in the top-line analyses:

Study conduct:

- Relevant eligibility deviations (Table and Listing)

Subject population:

- End of Treatment Summary
- Accrual by Region
- Accrual by stratification factors at randomization
- Demographic Characteristics Summary
- IVRS Stratification Factors Summary
- Baseline Myeloma Characteristics Summary (SI units)
- Other Baseline Laboratory Measurements Summary
- Risk Factors Results Summary
- Prior Systemic Anti-myeloma Therapy
- Prior Systemic Therapy Drugs Summary
- Refractory Status to Most Recent Line of Therapy Summary
- Time from Diagnosis to Randomization Summary
- Baseline Physical Measurements Summary

Extent of exposure:

- Number of Cycles Summary
- Elotuzumab Dose Intensity Summary
- Dexamethasone Dose Intensity Summary
- Pomalidomide Dose Intensity Summary
- Elotuzumab Delay Summary
- Elotuzumab Omission Summary
- Elotuzumab Infusion Interruption Summary
- Pomalidomide Reduction Summary
- Pomalidomide Interruption Summary

Tumor response:

- Best Overall Response
- Best Overall Response Odds Ratio and 95% CI in Subsets (Figure)

- Time to First Response Summary
- Kaplan-Meier Plot of Duration of Response

Progression free survival:

- Currentness of Follow-Up for PFS Summary
- PFS (ITT) Analysis
- Kaplan-Meier plot of PFS (ITT) (Figure)
- PFS (ITT) Analysis Adjusting for Different Baseline Covariates
- PFS (ITT) Hazard Ratio and 95% CI in Subsets (Forest plot)
- PFS (Secondary Def.) Analysis
- Kaplan-Meier plot of PFS (Secondary Def.) (Figure)
- PFS (Secondary Def.) Analysis Adjusting for Different Baseline Covariates
- PFS (Secondary Def.) Hazard Ratio and 95% CI in Subsets (Forest plot)

Overall survival:

- Currentness of Follow-Up for Overall Survival Summary
- Overall Survival Analysis
- Overall Survival Analysis Adjusting for Different Baseline Covariates
- Kaplan-Meier plot of overall survival (Figure)
- Overall survival Hazard Ratio and 95% CI in Subsets (Forest plot)

Safety:

- Hematologic Laboratory Test Results Summary of Worst Toxicity Grade - SI Units
- Renal and Liver Laboratory Test Results Summary of Worst Toxicity Grade - SI Units
- Chemistry Laboratory Test Results Summary of Worst Toxicity Grade - SI Units
- Other Laboratory Test Results Summary (BUN, DBILI, TPRO)
- Potential Drug Induced Liver Injury Cases Summary - SI Units
- Adverse Event Summary by CTC Grade Combined
- Related Adverse Event Summary by CTC Grade Combined
- Serious Adverse Event Summary by CTC Grade Combined
- Related Serious Adverse Event Summary by CTC Grade Combined
- Adverse Event Leading to Discontinuation Summary by CTC Grade Combined
- Related Adverse Event Leading to Discontinuation Summary by CTC Grade Combined
- Infusion Reaction Summary by Common Terminology Criteria
- Second Primary Malignancy Summary
- Deaths
- Deaths within 60 days of last study drug

Specific tables corresponding to these topics will be identified in a separate Data Presentation Plan.

[REDACTED]

[REDACTED]	[REDACTED]	[REDACTED]
[REDACTED]	[REDACTED]	[REDACTED]
[REDACTED]	[REDACTED]	[REDACTED]
